7.2.5 Infusion reactions and anaphylaxis

Patients should be assessed carefully for infusion-related reactions. Since it may not be apparent at the time whether a patient is having a reaction due to cytokine release or mast cell degranulation, and since NCI-CTCAE Version 4.02 criteria overlap for cytokine release syndrome, allergic reaction and anaphylaxis, it is proposed that:

- All infusion-related events are reported as individual AEs (e.g. fever, nausea, myalgia or hypotension). Time of onset and worst grade (according to NCI-CTCAE Version 4.02) should be noted for each event.
- Subsequently, infusion-related events associated with an elevation in serum tryptase will be categorised according to the grading criteria outlined in Appendix 5 for IgE-associated mast cell degranulation (anaphylaxis).
- Urticaria is a characteristic feature of anaphylaxis and is to be regarded with suspicion. Patients who experience any of the following events should have additional samples taken as outlined below:

- Urticaria; symptoms/signs suggestive of mast cell degranulation; a suspected anaphylactic reaction; signs and symptoms suggestive of a severe allergic-type reaction; severe infusion-related symptoms necessitating interruption or discontinuation of the infusion.

Additional Samples:

NB: the additional samples outlined below can replace the existing samples in the Schedule of assessments, if the timepoints overlap. Please take all other samples as per schedule in section 7.6.

- Serum tryptase (immediately*, 2 and 6** hours post onset),
- BAT assay (immediately* post onset, in replacement of existing 2 hour timepoint in schedule),
- PK (immediately*, 2 and 6** hours post onset),
- [REDACTED]

*Or as soon as possible post onset.

**6 hour samples may be omitted *if* impracticable and clinical suspicion of systemic toxicity is low. This is at the discretion of the treating clinician.

- If a patient clearly shows a pattern of simple urticaria with two separate infusions, with no other systemic signs or symptoms and no other features of anaphylaxis (including normal tryptase results and normal BAT assay results) then, following discussion and confirmation with Sponsor, there may be no requirement for additional samples.
- [REDACTED]
- [REDACTED]
- [REDACTED]
- Infusion-related events without an elevation in serum tryptase will be categorised as cytokine release syndrome according to NCI-CTCAE Version 4.02 (Appendix 6).

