1 PROTOCOL SYNOPSIS

Study title: A Cancer Research UK Phase I study of MOv18 IgE, a first in class chimeric IgE antibody against folate receptor- α , in patients with advanced solid tumours.

Short title: Phase I study of MOv18 IgE.

Study Objectives and Endpoints:

Primary Objectives	Endpoints
To assess the safety and tolerability of MOv18 IgE	
 • AEs and DLTs • Dose-independent significant toxicity (Section 3.3.2) • SAEs • Laboratory parameters 
AEs, SAEs and laboratory abnormalities will be graded according to NCI-CTCAE Version 4.02.
 
Causality of AEs/SAEs will be assessed by the investigator. Infusion-related events will be categorised as due to IgE-mediated mast cell degranulation (anaphylaxis) or cytokine release syndrome.

Secondary Objectives	Endpoints
To determine a recommended dose for Phase II evaluation.	The recommended phase II dose (RP2D) will be based on safety data (the Maximum Tolerated Dose; see definition in Section 3.4), and/or efficacy data (the dose at which evidence of anti-tumour activity is seen), and/or pharmacodynamic data, or will be the maximum evaluated dose (50 mg).
To document possible anti-tumour activity in patients treated at doses likely to be pharmacologically active	Best response (according to RECIST 1.1) in patients receiving at least one dose of MOv18 IgE CA125 response in patients with elevated CA125 at baseline
To describe the pharmacokinetics of MOv18 IgE	Serum concentrations of MOv18 IgE
Tertiary Objectives	Endpoints
	      

Study design: This is a multi-centre, first in human, Phase I, open label, dose escalation study. Approximately 25 evaluable patients with advanced, unresectable solid tumours expressing the FR α for which no alternative therapy is felt to be appropriate will be entered into this study.

Study treatment: MOv18 IgE will be administered as an IV infusion. Patients in all cohorts will receive a total of six doses of MOv18 IgE at 1-week intervals over a 6 week 'Initial Treatment Period'.

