3.3 Definition of dose limiting toxicity

Therapeutic IgGs such as trastuzumab, alemtuzumab or rituximab, and related proteins commonly cause infusion-related reactions. These reactions are thought to be due to cytokine release and typically are most frequent and severe with the first infusion, declining in incidence and severity thereafter. Such reactions are generally managed by slowing or interrupting the infusion. It is possible that MOv18 IgE will cause these non-specific infusion-related reactions, which are biologically distinct from anaphylaxis, although it can be difficult to distinguish them clinically.

Despite pre-clinical evidence suggesting otherwise, it is possible that MOv18 IgE may also cause anaphylaxis due to basophil and/or mast cell degranulation. Such a reaction would be predicted to persist and probably worsen with subsequent infusions. Slowing or interrupting the infusion would typically be insufficient to control such a reaction and systemic therapy, including administration of adrenaline, might be needed.

Clinically, the symptoms, signs and onset of typical cytokine release-type infusion reactions are very similar to those associated with IgE-mediated basophil and/or mast cell degranulation/anaphylaxis and it may be difficult to distinguish these different types of acute reaction in a patient receiving their first dose. However, the presence of urticaria is almost universal in reactions due to mast cell degranulation, but is not typical of infusion reactions seen with protein-based therapeutics such as IgGs (although it can occur). Importantly, emerging data from the CRUKD14001 study indicate that urticaria without systemic symptoms is common with MOv18 IgE and does not necessarily indicate the onset of anaphylaxis. Serum tryptase elevation (a marker of mast cell degranulation) would not be expected to occur with cytokine release-type infusion reactions (Cheifetz *et al.*, 2003), and for this study is considered critical in distinguishing these two types of reactions clinically.

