3.3.1 Dose limiting toxicity (DLT)

Dose limiting toxicity is defined as any of the following events occurring in the first 3 weeks of IMP administration that are considered to be probably or highly probably related to MOv18 IgE:

(For dose-independent significant toxicity, see Section 3.3.2)

Non-haematological toxicity

- Any other drug-related non-haematological Grade 3 or 4 toxicity EXCLUDING:
 - Grade 3 or 4 nausea or vomiting, in patients who have not received optimal treatment with anti-emetics
 - Grade 3 or 4 diarrhoea in patients who have not received optimal treatment with anti-diarrhoeals e.g. loperamide and/or codeine
 - Transient Grade 3 biochemical abnormalities that are asymptomatic and considered not to be clinically significant
 - Grade 3 fatigue
- Fatal event

Haematological toxicity

- Grade 4 neutropenia ($ANC < 0.5 \times 10^9/L$) for ≥ 5 days duration *see note
- Febrile neutropenia (fever of unknown origin without clinically or microbiologically documented infection with Grade 3 or 4 neutropenia [$ANC < 1.0 \times 10^9/L$] and fever $\geq 38.5^\circ C$)
- infection (documented clinically or microbiologically) with Grade 3 or 4 neutropenia ($ANC < 1.0 \times 10^9/L$);
- Grade 4 thrombocytopenia (platelets $< 25 \times 10^9/L$)
 - a) for ≥ 5 days *see note, or
 - b) associated with active bleeding, or
 - c) requiring platelet transfusion.

* In the event of a Grade 4 neutropenia or Grade 4 thrombocytopenia, a full blood count must be performed at least five days after the onset of the event to determine if a DLT has occurred. Continue to monitor the patient closely until resolution to Grade 3 or less.

Note that:

- Isolated cutaneous toxicity (urticaria or other skin symptoms/signs) without any associated systemic symptoms or signs and without serum tryptase elevation may not be considered a DLT, if agreed by the Trial Steering Group (TSG) (see Section 3.6 for information regarding the Trial Steering Group). Such patients require premedication (at least for the first subsequent dose) and very close observation if they are given further doses of MOv18 IgE;

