5.3.1 Study drug administration

All patients will receive their first two doses of MOv18 IgE as an IV infusion over 90 minutes (+/-15 mins). A shorter infusion time for subsequent doses of 60 minutes (+/-10 mins) will be allowed if no infusion-related reactions or other allergic reactions are encountered after two doses have been administered. A longer infusion time for subsequent infusions will also be allowed if required in order to manage infusion related cutaneous toxicity. Patients should remain in the clinic for observation for at least one hour after every dose of MOv18 IgE.

The study will be undertaken at investigational centres staffed and equipped to manage medical emergencies and with intensive care facilities. If the patient experiences an event related to study drug that requires intensive clinical care, the Sponsor must be notified immediately.

Patients will be admitted overnight after the first two doses to facilitate intensive safety monitoring procedures. At the investigator's discretion, the requirement for admission may be waived for the second dose if the patient experiences no clinically important adverse events related to MOv18 IgE during the infusion and observation period.

Pre-medication will be administered prior to the first dose in later cohorts if deemed medically appropriate. See Section 5.4

The patient will be intensively monitored during their first two infusions, with measurement of vital signs (blood pressure, pulse rate and temperature) every 15 minutes from the start of the infusion until 30 minutes after completion of the infusion. If no changes are seen, during the first two infusions, then for subsequent infusions vital signs will be assessed 15 minutes and 30 minutes after completion of the infusion. Continuous monitoring with a pulse oximeter is required throughout each infusion until 30 minutes after completion.

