If the patient experiences symptoms suggestive of an infusion-related reaction or cytokine release (such as fever, chills, and myalgia), the infusion must be slowed or interrupted and the patient must be treated with oxygen, paracetamol, antihistamines, fluid resuscitation and/or steroids, as clinically indicated. If the reaction does not respond to these conservative measures or is > Grade 2 in severity, the algorithm for the treatment of anaphylaxis must be followed (Appendix 4). Note that for the purposes of this protocol, infusion-related symptoms and signs (such as fever, myalgia, and hypotension) will be recorded and graded individually according to NCI-CTCAE Version 4.02. Grading of systemic mast cell degranulation (anaphylaxis) is defined in Appendix 5 and grading of cytokine release syndrome is defined in Appendix 6, but the distinction between these two events and grading of these events will be performed only in retrospect when results of serum tryptase assays are available, and will thus not be relevant for the management of acute events at the time of infusion. A blood test for measurement of serum tryptase will be taken on completion of all infusions. Additional blood samples for serum tryptase levels should be taken in patients who experience a suspected anaphylactic reaction, such as urticaria and/or severe infusion-related symptoms necessitating interruption or discontinuation of the infusion. Additional samples for serum tryptase should also be taken for patients with a positive skin prick test (see study lab manual and protocol section 7.2 for time points). For details on grading and reporting of infusion-related events and anaphylaxis see Section 7.2.5.

The following medications must be available at the bedside for use in case of an immune-mediated reaction: epinephrine (0.5-1mL IM injection 1:1000), chlorphenamine 10 mg IV/IM injection, paracetamol 1 g orally, hydrocortisone 200 mg IM or IV; oxygen (see 16.4 Appendix 4: Treatment of Anaphylaxis).

For patients who are enrolled in an intra-patient escalation cohort, and receive a higher dose in Cycle 2, the following additional measures will apply:

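### Under 7.2.5 a skin-only infusion reaction with a negative tryptase is counted and graded as cytokine release syndrome, although the protocol elsewhere describes it apart

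*Protocol*

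**What the plan says.** The protocol synopsis and 3.1, in the cell that lists the primary endpoints, state: "Infusion-related events will be categorised as due to IgE-mediated mast cell degranulation (anaphylaxis) or cytokine release syndrome". Neither mentions tryptase or gives a third category.

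Section 7.2.5 makes the rule operational. It first requires that "All infusion-related events are reported as individual AEs". Events with a raised tryptase are then graded by Appendix 5 as anaphylaxis. For the rest: "Infusion-related events without an elevation in serum tryptase will be categorised as cytokine release syndrome according to NCI-CTCAE Version 4.02 (Appendix 6".

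Other sections describe skin-only reactions separately:

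- Section 3.3 reports that "urticaria without systemic symptoms is common with MOv18 IgE and does not necessarily indicate the onset of anaphylaxis", and says that urticaria "is not typical of infusion reactions seen with protein-based therapeutics such as IgGs (although it can occur".
- Section 3.3.1 has a separate DLT note for this pattern: "Isolated cutaneous toxicity (urticaria or other skin symptoms/signs) without any associated systemic symptoms or signs and without serum tryptase elevation".
- Section 5.3.1 names it when it deals with infusion time: "A longer infusion time for subsequent infusions will also be allowed if required in order to manage infusion related cutaneous toxicity".
- Appendix 5 also describes urticaria on its own as common and manageable.

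On the assay, 5.3.1 says: "A blood test for measurement of serum tryptase will be taken on completion of all infusions". It adds that anaphylaxis and CRS are told apart and graded only afterwards, once tryptase results exist. Appendix 5 requires a positive assay for anaphylaxis and Appendix 6 a negative one for CRS. Table 4 footnote (h) requires results before the second and third doses. Later samples, and maintenance samples under Table 5 footnote (d), may be analysed if the investigator asks in response to symptoms.

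**The concern.** A closed two-way rule needs two categories that between them fit every event. Here one of them is a residual. Whatever is not tryptase-positive becomes CRS, whether or not it resembles a cytokine reaction. The protocol's own emerging data say that a third pattern, urticaria without systemic symptoms, is common with this antibody.

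What is at stake is how the CRS category reads in the study report. For a first-in-class IgE, a count of CRS made up partly of skin-only reactions would misdescribe the safety profile. A reader could not tell from that count how many patients had a systemic cytokine-type reaction.

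**Working it through.** There is no figure to reproduce. The protocol gives no rate for urticaria beyond calling it common, so the check sets the passages side by side for each type of event.

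1. **Tryptase raised.** Section 7.2.5 and Appendix 5 both lead to anaphylaxis. This is consistent.

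2. **Assayed and negative, with systemic symptoms or signs.** Section 7.2.5 leads to CRS. Appendix 6 defines CRS by nausea, headache, tachycardia, hypotension, rash and shortness of breath, and requires a negative assay. This is consistent.

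3. **Assayed and negative, skin only.** Section 7.2.5 again leads to CRS, and the two-way rule offers nothing else. Three things do not fit:
   - Sections 3.3 and 3.3.1 and Appendix 5 describe this pattern apart from anaphylaxis, and 3.3 also separates urticaria from the typical cytokine-type reaction.
   - Appendix 6 makes a negative assay a necessary condition for CRS. It does not say that a negative assay is enough, whereas 7.2.5 uses it as if it were.
   - The grade follows the label. Appendix 6 Grade 2 covers a reaction that needs therapy or interruption and settles promptly, with antihistamines among its examples. Urticaria treated that way would be recorded as Grade 2 CRS.

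4. **Sample drawn but not assayed.** Appendix 5 needs a positive result and Appendix 6 a negative one, and 5.3.1 makes the distinction only when results are available. The event meets neither definition and has no category, although the synopsis and 3.1 imply that every event has one. The on-request wording in Table 4(h) and Table 5(d) makes such events possible.

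5. **Where the label is used.** Section 13.2 tabulates adverse events by body system and worst grade, so urticaria remains visible as its own event. The DLT definition in 3.3.1, the escalation rules in Table 2 and the anaphylaxis assessment in 3.4.2 use no count of CRS. Section 5.5.1 points to Appendix 6 when it refers other infusion reactions to the Trial Steering Group, so it belongs among the passages to be read together.

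**The case against.** The strongest defence is that the tryptase rule is a deliberate convention. Section 7.2.5 notes that the CTCAE criteria for CRS, allergic reaction and anaphylaxis overlap, and 3.3 treats tryptase as the critical discriminator. Appendix 6 lists rash among the features of CRS, 3.3 accepts that urticaria can occur in infusion reactions, and no visible passage forbids calling isolated urticaria CRS. All of this stands. It makes the problem a misfit between passages, not a flat contradiction. It does not remove the misfit, because a rule built to separate two reactions has no place for a third that the same protocol describes as common.

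A reader might also infer that unassayed events are coded as CRS, since they too lack a demonstrated elevation. The documents do not support that. Section 5.3.1 ties the distinction to available results, and 7.2.5 cites Appendix 6, which requires a negative assay. Such events are left without a category. They should also be few, because symptoms are the stated reason for requesting an assay, and urticaria or suspected anaphylaxis calls for extra tryptase samples under 7.2.5.

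Nor do the synopsis and 3.1 themselves code by tryptase. They supply only the two-way rule, and the tryptase criterion comes from 7.2.5 and the appendices.

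Finally, three bullets just before the quoted rule in 7.2.5 are redacted, as is the body of Table 6. An exception for urticaria, or a provision for batch assay, may be there.

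**Conclusion.** The point holds as a minor one. On the visible text, skin-only reactions with a negative tryptase are counted and graded as CRS, which mixes them with systemic cytokine-type reactions in the derived category. As a secondary point, events without an assay result have no category, contrary to the closed two-way rule.

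The size in patients cannot be stated, because the protocol gives no frequency. The effect is confined to the derived CRS category. Because the categorisation sentence stands beside the primary endpoints, a reader might infer that the primary safety analysis or dose decisions are distorted. They are not: individual adverse events are graded and tabulated separately, and DLT decisions and the anaphylaxis rule are unaffected.

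The conclusion assumes that the redacted bullets in 7.2.5 contain no exception for isolated skin reactions. The secondary point also assumes that Table 6 does not already require the samples to be assayed.

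**What to change.** Reconcile the synopsis, 3.1 and 7.2.5 with 3.3.1 and Appendices 5 and 6:

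1. In 7.2.5, replace the condition of no elevation with the Appendix 6 condition, a negative serum tryptase assay.
2. Report mutually exclusive categories:
   - anaphylaxis: tryptase-positive, graded by Appendix 5;
   - CRS: tryptase-negative with systemic symptoms or signs, graded by Appendix 6;
   - isolated cutaneous reaction, defined as in 3.3.1: no systemic symptoms or signs and no tryptase elevation;
   - unclassified: any remaining event, with the reason.
3. Unless Table 6 already provides for it, state that the tryptase sample already drawn is assayed before the final analysis for every infusion with an infusion-related event.

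State that these are reporting categories only, and that they do not change which reactions are managed or referred under 5.5.1.

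The cost is a few lines of wording and a few assays on samples already drawn, with no new blood draws. Separating the second category from the third needs a judgement on systemic signs, which 3.3.1 already asks for.

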7.3 Evaluations at First Post-treatment Safety Assessment (28 ±7 days after final dose)

Evaluations at the First Post-treatment Safety Assessment must be performed 28 ±7 days after the final infusion of MOv18 IgE. The following investigations should be done:

- **Symptom-directed physical examination**
- **WHO performance status**
- **Weight**
- **Vital signs**, if clinically indicated
- **ECG**

- **Blood sample for clinical laboratory tests** – Haematology and Biochemistry parameters as detailed in Section 7.1.4
- **Urine sample for urinalysis** – glucose, protein and blood
- **Assessment of AEs and concomitant treatments**
- **Assessment of disease response**: if not performed within previous 28 days per RECIST based on clinical examination, tumour marker, and CT/MRI for patients with measurable disease. Response will be assessed by RECIST 1.1 criteria (see Appendix 3), as well as by CA125 or other tumour marker (Rustin, 2003) if applicable.
- **Tumour marker**, if appropriate for tumour type
- **Research blood samples** as described in Table 6 Summary of PK and PD Assessments (see Section 8.3).

Patients who receive MOv18 IgE as a skin prick test only should be followed for safety until resolution or stabilisation of any AEs/SAEs associated with MOv18 IgE.

7.4 Evaluations at Second Post-treatment Safety Assessment (70 ±14 days after final dose)

- **Symptom-directed physical examination**
- **Assessment of AEs**

For patients who are unable to attend in person for this visit due to concurrent illness, progressive disease or other reasons, the safety assessment may be made by telephone and the sample for PK assessment omitted.

7.5 Follow-up of drug-related AEs

Patients who receive any dose of IV MOv18 IgE will be followed for safety reporting until the Second Post-treatment Safety Assessment. If any drug-related AEs and SAEs (i.e. those considered to have a highly probable, probable or possible causal relationship to MOv18 IgE) are present at this assessment, the patient will be followed up at least monthly afterwards until resolution to baseline or stabilisation of these events, unless the patient starts another anti-tumour treatment. If the patient is experiencing no drug-related AEs at the Second Post-treatment Safety Assessment then no follow-up is required.

Patients who receive MOv18 IgE as a skin prick test only should also be followed for safety at least monthly until resolution or stabilisation of any treatment-related AEs/SAEs.

7.6 Schedule of events

Table 4: Schedule for Initial Dosing Period

Observation/Investigation	Screening/Baseline		Initial Dosing Period (first 6 doses) Evaluations for each 3 week cycle (3 doses)			First Post-treatment Safety Assessment	Second Post-treatment Safety Assessment	
	Day -28 to Day 1 Pre-dose		Day -7 to Day 1 Pre-dose	Day 1 ± 2 days	Day 8 ± 2 days	Day 15 ± 2 days	28 days ± 7 days after final dose	70 days ± 14 days after final dose
FRa IHC test on archival tumour tissue	X ^a							
Demographics	X							
Medical history	X							
Adverse event evaluation			From date of informed consent, continually review			X ^p	X ^p	
Concomitant treatments			From date of informed consent, continually review					
Radiological disease assessment	X		Every 6 weeks			X ^q		
Clinical disease assessment (if applicable)	X		Repeat as clinically indicated			X		
Tumour markers e.g. CA125 (if applicable)	X		Every 3 weeks if clinically appropriate for tumour type			X		
Physical examination	Complete		Symptom-directed, as clinically indicated			Symptom-directed		
WHO performance status	X		X	X	X	X		
Vital signs (BP, pulse rate, temperature)	X		X ^g	X ^g	X ^g	If clinically indicated		
Height	X							
Weight	X						X	
Electrocardiogram (ECG)	X		X ^s	X ^s	X ^s	X		
Tumour biopsy ^b	X		Once between C1D8 and C2D15 ^u					
Blood sample for clinical laboratory tests ^c		X	X	X	X	X		

Observation/Investigation	Screening/Baseline		Initial Dosing Period (first 6 doses) Evaluations for each 3 week cycle (3 doses)			First Post-treatment Safety Assessment	Second Post-treatment Safety Assessment
	Day -28 to Day 1 Pre-dose	Day -7 to Day 1 Pre-dose	Day 1 ± 2 days	Day 8 ± 2 days	Day 15 ± 2 days	28 days ± 7 days after final dose	70 days ± 14 days after final dose
Urine sample for urinalysis		X	X			X	
Pregnancy test (if applicable) ^d		X					
Blood for serum IgE (SIgE) ^e		X					
MOv18 IgE skin prick test ^f			X	X	X		
MOv18 IgE administration			X	X	X		
1 h observation post-administration			X	X	X		
Overnight stay after MOv18 IgE infusion			Cycle 1 ^t	Cycle 1 ^t			
Blood for serum tryptase test ^h		X	X	X	X		
Blood sample for PK ⁱ			Cycle 1 ^t	Cycle 1			
[REDACTED]	[REDACTED]	[REDACTED]	[REDACTED]	[REDACTED]	[REDACTED]	[REDACTED]	[REDACTED]
Blood for basophil activation test (BAT) assay ^k		X	Cycle 1 ^t		Cycle 1		
[REDACTED]	[REDACTED]	[REDACTED]	[REDACTED]	[REDACTED]	[REDACTED]	[REDACTED]	[REDACTED]
[REDACTED]	[REDACTED]	[REDACTED]	[REDACTED]	[REDACTED]	[REDACTED]	[REDACTED]	[REDACTED]
[REDACTED]	[REDACTED]	[REDACTED]	[REDACTED]	[REDACTED]	[REDACTED]	[REDACTED]	[REDACTED]
[REDACTED]	[REDACTED]	[REDACTED]	[REDACTED]	[REDACTED]	[REDACTED]	[REDACTED]	[REDACTED]

(a) FR- α staining of archival tumour material may be performed >28 days prior to treatment on Day 1 and before obtaining consent for the main study.

(b) [REDACTED]

CONFIDENTIAL

(c) **Blood sample for clinical laboratory tests:** Haematology, biochemistry and coagulation screens should be performed for the assessment of eligibility during Screening (Day -7 to pre-dose on Day 1). Measurements performed before Day -14 may be accepted by the CDD to demonstrate eligibility if repeat testing is logistically difficult for the patient and is not considered necessary medically in the opinion of the Investigator or CDD.

Haematology and biochemistry should be performed within the 24 h (± 4 h) prior to each dose.

In the event of a Grade 4 neutropenia or Grade 4 thrombocytopenia, a full blood count must be performed at least five days after the onset of the event to determine if a DLT has occurred. Continue to monitor the patient closely until resolution to Grade 3 or less (see Section 3.3 Dose Limiting Toxicity).

(d) **Pregnancy test** for female patients of child bearing potential.

(e) 1 mL blood sample for assessment of **serum IgE** will be taken at baseline only.

(f) **MOv18 IgE skin prick test** on inner forearm with positive histamine control and negative saline control to be performed at the bedside by a specifically trained nurse. Response to the skin prick test should be assessed at 15, 30 and 60 mins post initiation of the skin prick test, prior to the start of every infusion of MOv18 IgE (see Appendix 8 for test method and instructions on interpretation of results).

(g) **Vital signs (BP, pulse rate and temperature)** should be performed for each infusion of MOv18 IgE within the 30 min (± 5 min) pre-dose, every 15 min (± 5 min) during the first and second infusions, 15 min (± 5 min) and 30 min (± 5 min) after completion of each infusion, and before discharge from the clinic. For the first infusion only, vital signs are additionally required (± 10 min) at 1h, 2h, 4h, 8h, 12h, 18h and 24h after completion of the infusion, and as clinically indicated. Monitoring with a pulse oximeter is required continuously throughout each infusion until 30 min after completion of the infusion. For intra-patient dose escalation cohorts, these assessments are to also be performed on Cycle 2 Day 1.

(h) 1 mL blood sample for 200 μ L serum for measurement of **serum tryptase** at baseline and on completion of every infusion of MOv18 IgE. Additional samples may be taken in response to a positive skin prick test or in patients who experience a suspected anaphylactic reaction, such as urticaria or severe or infusion-related symptoms necessitating interruption or discontinuation of the infusion (see protocol section 7.2.1 and 7.2.5 for details of when to take these samples). Samples will be analysed and reported prior to next dose for 2nd and 3rd doses. Subsequent samples can be analysed on request of the Investigator in response to clinical symptoms and reported prior to next dose.

(i) 3.5 mL blood sample for 1-2 mL serum for **PK assessment of circulating MOv18 IgE** at 7 time points: Pre-dose on Cycle 1 Day 1 (within 24 h of infusion), 30 min (± 5 min)*, 2 h (± 30 min), 4 h (± 30 min), 6 h (± 30 min), 24 h (± 2 h), and possibly* at 48 h (± 2 h) post-dose; Cycle 1 Day 8 Pre-dose; (total blood volume ~ 25 mL). If a time point has been missed, a sample should be taken as soon as possible and the time recorded. *The 30 min (± 5 min) sample may be replaced by the 48h (± 2 h) post-dose sample at higher dose cohort levels (refer to the study laboratory manual for which sample to take). Additional samples should be taken at 0, 2 and 6 hours following a suspected anaphylactic/urticarial reaction or positive skin prick test (see protocol section 7.2.1 and 7.2.5 for details).

(j)

(k) 6 mL blood sample for **basophil activation test (BAT)** at Day -7 to Pre dose Cycle 1 Day 1 and 2 h (± 30 min) after the end of infusion of MOv18 IgE at the first and third infusions (Cycle 1 Day 1 and Cycle 1 Day 15) (total blood volume 18 mL). Additional samples should be taken immediately (0 hours) following a suspected anaphylactic reaction, urticarial, or severe infusion-related symptoms necessitating interruption or discontinuation of the infusion or positive skin prick test (see protocol section 7.2.1 and 7.2.5 for details). For intra-patient dose escalation cohorts, a sample will also be taken on Cycle 2 Day 1, 2 h (± 30 min) after the end of infusion of the higher dose of MOv18 IgE.

- (l) [REDACTED]
- (m) [REDACTED]
- (n) [REDACTED]
- (o) [REDACTED]
- (p) Monthly **follow-up** required ONLY for those AEs and SAEs considered drug-related (highly probable, probable or possible) and present at the Second Post-treatment Safety Assessment. Monthly follow-up to continue until resolution, return to baseline, stabilisation or patient starts another anti-cancer treatment.
- (q) All patients, who are removed from the study for reasons other than progressive disease, must be re-evaluated at the time of treatment discontinuation, unless a **tumour assessment** was performed within the previous four weeks.
- (r) For patients unable to attend in person for the **Second Post-treatment Safety Assessment** due to concurrent illness, progressive disease or other reasons, the safety assessment may be made by telephone and the sample for PK assessment omitted.
- (s) ECG to be performed after completion of the infusion.
- (t) For intra-patient dose escalation cohorts, these assessments are to also be performed on Cycle 2 Day 1.
- (u) For intra-patient dose escalation cohorts, the post dose biopsy should be performed following at least the first dose in Cycle 2 where possible.

Table 5: Schedule for Maintenance Dosing Period

Observation/Investigation	Screening/ Baseline	Initial Dosing Period	Maintenance Dosing Period (MOv18 IgE dosing every 14 ± 2 days)			First Post- treatment Safety Assessment	First Post- treatment Safety Assessment		
			7th dose	8th dose	9th dose	28 days ± 7 days after final dose	70 days +/- 14 days after final dose		
Adverse event evaluation			Continually review			As in Table 4	As in Table 4		
Concomitant treatments			Continually review						
Radiological disease assessment	As in Table 4	As in Table 4	Every 6 weeks						
Clinical disease assessment (if applicable)			Repeat as clinically indicated						
Tumour markers e.g. CA125 (if applicable)			Repeat as clinically indicated						
Physical examination			Symptom-directed, as clinically indicated						
WHO performance status			X	X	X				
Vital signs (BP, pulse rate, temperature) ^a			X	X	X				
ECG			X						
Bloods for haematology & biochemistry ^b			X	X	X				
Urine sample for urinalysis			X						
MOv18 IgE skin prick test ^c			X	X	X				
MOv18 IgE administration			X	X	X				
1 h observation post-administration			X	X	X				
Blood for serum tryptase test ^d			X	X	X				

- (a) **Vital signs (BP, pulse rate and temperature)** should be performed within the 30 min (±5min) pre-dose, 15 min (±5min) and 30 min (±5min) after completion of the infusion and before discharge from the clinic at every infusion of MOv18 IgE and as clinically indicated. Monitoring with a pulse oximeter is required continuously throughout the infusion until 30 min after completion of the infusion.
- (b) **Blood sample for Clinical laboratory tests:** Haematology and biochemistry should be performed within 24 h (± 4 h) before dosing for every infusion of MOv18 IgE. In the event of a Grade 4 neutropenia or Grade 4 thrombocytopenia, a full blood count must be performed at least five days after the onset of the event. Patients should be monitored closely until resolution to Grade 3 or less (see Section 3.3 Dose Limiting Toxicity).
- (c) **MOv18 IgE skin prick test** on inner forearm with positive histamine control and negative saline control to be performed at the bedside by a specifically trained nurse. Response to the skin prick test should be assessed at 15, 30 and 60 mins post initiation of the skin prick test, prior to the start of EVERY infusion of MOv18 IgE (see Appendix 8 for test method and instructions on interpretation of results). Additional blood samples should be taken in case of a positive test (see Section 7.2.1 and footnotes to Table 4).

CONFIDENTIAL

(d) 5 mL blood sample for 200 µL serum for measurement of serum **tryptase** at baseline and on completion of every infusion of MOv18 IgE. Additional samples may be taken in response to a positive skin prick test or in patients who experience a suspected anaphylactic reaction, urticarial, or severe infusion-related symptoms necessitating interruption or discontinuation of the infusion (see protocol section 7.2.1 and 7.2.5 for details of when to take these samples). Samples can be analysed on request of the Investigator in response to clinical symptoms and reported prior to next dose.

